## Study design

This will be an open, prospective, non-randomized, controlled parallel-group multicenter study to document the outcome of treatment with the OsseoSpeed™ implant in the maxilla of postmenopausal women with systemic osteoporosis/osteopenia. Two groups will be included in the study: *Group A (osteoporosis/osteopenia)* consisting of postmenopausal women with low BMD values (T-score  $\leq -2$ ) and *Group B (control)* consisting of postmenopausal women with normal BMD values (T-score  $\geq -1$ ). Each subject will receive 2-8 splinted implants in the maxilla and two-stage surgery will be used.

A total of 104 subjects fulfilling all of the inclusion criteria and none of the exclusion criteria will be included. Fifty-two subjects will be included in group A (osteoporosis/osteopenia group) and fifty-two in group B (control). Four centers will be involved in the study, each center treating 13 osteoporotic/osteopenic subjects and 13 control subjects.

The study will be a five-year follow-up study comprising of 13 visits:

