## Study population

### *Inclusion criteria*

For inclusion in the study subjects must fulfill all of the following criteria:

1. Provision of informed consent
2. Postmenopausal women aged 60 years and over
3. In need of 2-8 implants in maxilla
4. A history of edentulism in the area of implant treatment of at least 6 months.
5. A BMD value suitable either for group A **or** group B:

**Group A (Osteoporosis/osteopenia):** BMD at least 2 standard deviations below mean peak bone density of young adults for the spine and total hip (T-score $\leq$ -2SD). Absolute values (g/cm^2) will be used.

**Group B (Control):** BMD not more than 1 standard deviation below mean peak bone density of young adults for the spine and total hip (T-score $\geq$ -1SD). Absolute values (g/cm^2) will be used.

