## Statistical methods

The primary objective is to test the hypothesis that the alteration in MBL from prosthetic restoration to the 5-year follow-up visit is equal (i.e. a two-sided hypothesis) in patients in group A and in group B. The hypothesis will be tested by means of the Wilcoxon rank sum test. A p-value less than 5% at the 5-year follow-up visit will be considered statistically significant. In addition, the time to certain degrees of alterations will be estimated by means of Kaplan-Meier plots and the hypothesis that the time is equal in group A and B will be tested by means of the log-rank test.

The secondary objectives are to test:

- The hypothesis that the survival rate is equal among implants on patients in group A and B by means of the Fisher's exact test (i.e. implant level). Furthermore, the time to implant loss will be estimated by means of Kaplan-Meier plots and the hypothesis that the time is equal in group A and B will be tested by means of the log-rank test.
- The hypothesis that the proportion of survived implants is equal in patients in group A and B by means of the Wilcoxon rank sum test (i.e. patient level).
- The hypothesis that the condition of peri-implant mucosa is equal in patients in group A and B by means of the Wilcoxon rank sum test.

The evaluation of the correlation between skeletal and maxillary BMD will be estimated by means of the Spearman's rank correlation coefficient on patient level.

All safety variables will be summarized by means of descriptive statistics. No hypotheses will be tested.

The hypothesis that the OHIP is equal in patients in group A and B will be tested by means of the Wilcoxon rank sum test

All hypotheses will be tested at all visits. P-values will be calculated but not called statistically significant except for the primary objective at the final visit.

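### The implant-level Fisher and log-rank tests of implant survival ignore clustering of 2-8 implants within a patient, and no precedence is set against the planned patient-level test (minor)

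*Combined protocol and SAP*

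**What the plan says.** All references are to the combined protocol and SAP.

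- **Data structure.** Under Study design: "Each subject will receive 2-8 splinted implants in the maxilla and two-stage surgery will be used". The inclusion criteria repeat the range: "In need of 2-8 implants in maxilla". Group is set by the patient's own BMD (inclusion criterion 5), so all implants in one mouth belong to the same group.
- **Implant-level survival.** Under Statistical methods, the first secondary bullet tests whether the "survival rate is equal among implants on patients in group A and B", using Fisher's "exact test (i.e. implant level").
- **Time to loss.** The same bullet continues that "the time to implant loss will be estimated by means of Kaplan-Meier plots", with a log-rank comparison of the groups. No unit is given for this part.
- **Patient-level survival.** The next bullet compares the share of implants surviving in each patient "by means of the Wilcoxon rank sum test (i.e. patient level").
- **Status of the p-values.** They are computed at every visit, and only the primary comparison at the final visit may be declared significant.

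No method for within-patient correlation is described for the Fisher or log-rank test, and no order is set among the survival analyses.

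**The concern.** Fisher's exact test and the ordinary log-rank test assume independent observations. Implants in one patient share bone, hygiene, medication, surgeon and, being splinted, a common restoration. It is therefore plausible that losses come in groups. Because the comparison is between patients, positive within-patient correlation increases the variance of the group difference, and neither test sees that increase.

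Implant survival is the first listed secondary objective, and the background section names dentists' fear of failure in osteoporotic patients as a motive for the study. A reader could be shown a small implant-level p-value beside a larger patient-level one, with no rule for choosing between them. For time to loss, the log-rank p-value is the only one planned.

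**Working it through.** **Plan's own figures.** The documents give no loss rate, intraclass correlation (ICC), power or event count for implant survival, so there is no figure to reproduce. The enrolment arithmetic agrees: 4 centers × (13 + 13) = 104, or 52 per group.

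**Inputs from the documents.** 52 + 52 patients; 2-8 implants each; implant-level Fisher; log-rank on time to loss.

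**Assumptions.** ICC 0.05, 0.1 or 0.2; marginal loss 1, 2 or 5%; implant counts uniform on 2-8 (mean 5) or on 2-4 (mean 3), with the same distribution in both groups; losses weighted to early follow-up; no dropout; log-rank run per implant. The nominal level of 5% is borrowed from the primary test.

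**Step 1, design effect.** DE = 1 + (E[m²]/E[m] − 1) × ICC. For counts uniform on 2-8, E[m] = 5 and E[m²] = (4+9+16+25+36+49+64)/7 = 29, so DE = 1 + 4.8 × ICC = 1.24, 1.48 and 1.96. A large-sample test that ignores this has true size 2 × (1 − Φ(1.96/√DE)), which is about 7.8, 10.7 and 16.2%.

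**Step 2, simulation.** Step 1 is a large-sample figure and Fisher's test is conservative with few events, so size was simulated directly. Losses were beta-binomial with equal per-implant risk in both groups, 4,000 replicates per setting. Entries are the percentage of trials with p < 0.05 at ICC 0.05 / 0.1 / 0.2; the Monte Carlo standard error is about 0.3-0.6 points.

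| Implants | Loss | Fisher, implant level | Log-rank, implant level |
|---|---|---|---|
| 2-8 | 1% | 3.1 / 4.6 / 7.7 | 6.6 / 8.9 / 12.5 |
| 2-8 | 2% | 4.6 / 7.7 / 11.7 | 6.9 / 10.5 / 15.3 |
| 2-8 | 5% | 5.9 / 8.5 / 13.0 | 7.2 / 10.2 / 15.4 |
| 2-4 | 1% | 0.9 / 1.4 / 2.2 | 3.4 / 4.4 / 6.0 |
| 2-4 | 2% | 3.0 / 3.2 / 5.0 | 6.0 / 6.8 / 9.2 |
| 2-4 | 5% | 4.5 / 5.7 / 7.5 | 6.0 / 7.7 / 9.7 |

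A repeat run at 2-8 implants and 5% loss gave Fisher 6.3 / 8.9 / 15.1% and log-rank 7.8 / 10.3 / 16.1%. Across runs, 2-8 implants with 2-5% loss therefore gives about 5-15% for Fisher and 7-16% for log-rank.

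**Step 3, where the problem fades.** Fisher is at or below 5% in 10 of the 18 settings. In the 12 settings with 1% loss or 2-4 implants, Fisher is at or below 5% in 9, while log-rank exceeds 5% in 10. With no clustering (ICC 0), Fisher is 0.4-4.1% and log-rank 2.4-5.1%, so neither is inflated.

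**Step 4, cluster-respecting alternatives.** With equal count distributions, the planned patient-level Wilcoxon had a size of 1.8-6.0% over the clustered settings. A log-rank score test with patient-clustered variance gave 4.5-4.9% at 2-8 implants and 5% loss. At 1% loss and ICC 0.05-0.2, roughly 17-49% of simulated trials had an arm with no losses. A log- or logit-link GEE has no finite group estimate there; a difference in proportions can still be computed as long as the other arm has a loss.

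**The case against.** The strongest reply is that the plan already separates implant-level from patient-level survival and includes a patient-level test that keeps close to its nominal level. It also says no secondary p-value will be declared significant, so no decision rests on Fisher or log-rank. The ICC, loss rate and implant counts above are assumptions, and since the risk/benefit section expects good results in both groups, the low-loss rows may apply.

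Most of this stands, and it rules out several stronger readings.

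- *That the survival analysis makes no allowance for clustering.* This is true of two tests, not of the analysis as a whole, because of the planned Wilcoxon.
- *That the log-rank unit is undetermined.* Fisher, the survival Wilcoxon and the Spearman analysis ("rank correlation coefficient on patient level") carry labels and the log-rank does not. But it sits in the implant-level bullet and concerns loss of implants, so the natural reading is clear. The gap is one of wording.
- *That the Wilcoxon is unsafe because the groups are not randomized.* The design is an "open, prospective, non-randomized, controlled parallel-group multicenter study", so mean implant counts could differ between groups. With rare losses the Wilcoxon mostly compares patients with any loss, which depends on count. But the documents give no sign of an imbalance. This justifies stratifying by count if one appears, not demoting the test.

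The reply does not make the Fisher or log-rank p-values valid when losses cluster. They will still be calculated at every visit, and time to loss has no stated counterpart that respects the clustering.

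**Conclusion.** The point holds as a minor one. As planned, the implant-level Fisher test, and the log-rank test on its natural reading, can give p-values that are too small if losses cluster. With 2-8 implants, 2-5% loss and ICC 0.05-0.2, a nominal 5% corresponds to about 5-15% for Fisher and 7-16% for log-rank. With losses near 1%, or few implants per patient, Fisher's own conservatism mostly hides the problem, while the log-rank usually remains inflated.

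The defect is established from the text; its size is conditional on the assumed ICC, loss rate and implant counts. A reader might infer that the trial's main conclusion or its survival findings are invalid. The documents do not support that: the primary comparison does not use these tests, a patient-level survival test is planned, and the secondary p-values will not be declared significant. What remains is the lack of a stated precedence among the survival results and of a valid test for time to loss.

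**What to change.** 1. Replace the implant-level Fisher p-value with a comparison of loss proportions on the difference scale, using patient-clustered variance. Alternatively, keep the Fisher result as descriptive only. Avoid relying on a log- or logit-link GEE, which fails when one arm has no losses.
2. Name one cluster-respecting test as the main survival comparison: either the planned patient-level Wilcoxon or the clustered comparison in item 1. If implant counts differ between groups, stratify the Wilcoxon by count.
3. State that the log-rank unit is the implant, and use a score or Cox test with patient-clustered robust variance. Use clustered standard errors for any Kaplan-Meier confidence bands.

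**Cost.** A few sentences of SAP wording and standard software; no new data and no change to care. P-values will be somewhat larger and intervals wider. The clustered tests are conservative when losses are very rare, with a true size of about 1-4% at 1% loss.

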**Study objectives**

*Primary objective*

The primary objective is to compare marginal bone level (MBL) alterations following treatment with the OsseoSpeed™ implant in the maxilla of post-menopausal women with and without systemic osteoporosis/osteopenia. Marginal bone level alterations will be evaluated by radiological assessments and MBL values at prosthetic insertion will be used as baseline.

*Secondary objectives*

The secondary objectives of the study are to evaluate (i.e. compare between the groups):

- Implant survival
- Implant stability, by using resonance frequency analysis (RFA)
- Condition of periimplant mucosa by assessment of Bleeding on Probing (BoP), Probing Pocket Depth (PPD) and Attachment Level (AL)
- Safety by recording of adverse events (AEs) and adverse device effects (ADEs)
- Patient reported outcomes by the Oral Health Impact Profile (OHIP)

*Additional objective*

The additional objective of the study is to evaluate the correlation between BMD in the skeleton (hip/spine) with BMD in the maxilla.

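### OHIP is compared between non-randomised groups with no baseline or covariate, so a pre-treatment difference would carry over, in part or in full, into the follow-up comparison

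*Combined protocol and SAP*

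**What the plan says.** Study objectives lists "Patient reported outcomes by the Oral Health Impact Profile (OHIP") among the secondary objectives to be compared between the groups. The whole analysis is one sentence in Statistical methods, where "The hypothesis that the OHIP is equal in patients in group A and B" is assessed with a Wilcoxon rank sum test and nothing further. The same section adds "All hypotheses will be tested at all visits", and says that no p-value will be called statistically significant except the primary one at the final visit.

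Study design describes an "open, prospective, non-randomized, controlled parallel-group multicenter study", with 52 women in each group and membership set by T-score. No matching, stratification or covariate is mentioned for any outcome.

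Marginal bone level (MBL) is handled differently. Study objectives states that "MBL values at prosthetic insertion will be used as baseline", and the primary test asks whether "the alteration in MBL from prosthetic restoration to the 5-year follow-up visit is equal (i.e. a two-sided hypothesis"). OHIP has no named baseline, no change score and no visit schedule.

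**The concern.** Without randomisation, nothing makes the two groups alike in oral-health burden at entry. Treatment need may run from 2 to 8 implants, and age starts at 60 with no upper limit, so starting OHIP could differ. A rank sum test on follow-up scores cannot separate a difference that arose after implant treatment from one the women brought with them.

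OHIP is also the between-group secondary outcome for which a remedy is readily available. Implant survival, implant stability and peri-implant mucosa have no value before an implant exists. OHIP can be completed at Visit 1 or 2, both of which precede surgery. At stake is how readers interpret the patient-reported comparison, together with some precision that a baseline score would add.

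**Working it through.** **Inputs from the plan.** There are 52 women per group (4 centers × 13 = 52; 4 × 26 = 104 in total, as stated). The plan gives no OHIP mean, SD, effect size or correlation, so there is no OHIP figure to reproduce.

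**Assumed inputs.** The starting OHIP difference d is 0.2 to 0.5 SD. The correlation r between pre-treatment and follow-up OHIP is 0.3 to 0.6. Scores have SD 1, and nothing after baseline separates the groups. Neither range comes from the documents.

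**Two models for the starting difference.**
- *Decays:* follow-up OHIP depends on group only through the starting score. Raw bias = r × d; bias after covariance adjustment (ANCOVA) = 0.
- *Persists:* both groups change in parallel. Raw bias = d; bias after ANCOVA = (1 − r) × d.

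| d, r | Raw, decays | ANCOVA, decays | Raw, persists | ANCOVA, persists |
|---|---|---|---|---|
| 0.2, 0.3 | 0.06 | 0 | 0.20 | 0.14 |
| 0.2, 0.6 | 0.12 | 0 | 0.20 | 0.08 |
| 0.5, 0.3 | 0.15 | 0 | 0.50 | 0.35 |
| 0.5, 0.6 | 0.30 | 0 | 0.50 | 0.20 |

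For any r between 0 and 1, ANCOVA has less bias than the raw comparison in both models. Where it leaves bias, that is 1 − r of the offset, or 40% to 70% here. It also reduces residual variance by r², which is 0.3² = 9% to 0.6² = 36%.

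**Scale at 52 per group.** The standard error of a raw difference is √(2/52) = 0.196 SD. The difference detectable with 80% power is (1.96 + 0.84) × 0.196 = 0.55 SD, so the upper end of the assumed bias approaches what the study could detect as a real effect.

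The share of p-values below 0.05 with no true effect is another way to express the size. For the Wilcoxon test, simulation gives about 6% to 31% when the offset decays and about 17% to 68% when it persists. ANCOVA stays near 5% when it decays. When it persists, the standard error is √[(1 − r²)(2/52 + d²/104)]:
- d = 0.2, r = 0.6: 0.08 / 0.158 = 0.51, about 8%.
- d = 0.5, r = 0.3: 0.35 / 0.193 = 1.81, about 44%.

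**Change score.** Its bias is 0 if the offset persists. If the offset decays, the bias has size (1 − r) × d, or 0.08 to 0.35 SD, which exceeds the raw bias whenever r is below 0.5. A switch to change scores alone is therefore not a safe remedy.

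**The case against.** The strongest reply has four parts.

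*No pre-treatment OHIP is shown.* This stands. A reader might infer one from the statement that every hypothesis is tested at every visit, but that cannot be literal: implant survival, mucosal condition and MBL change cannot be tested before implants exist. The descriptions of Visits 1 and 2 do not mention OHIP. Nor is their silence proof of absence, because the follow-up visit descriptions list no assessments either. The text also does not strictly exclude a change score. A comparison of levels is the natural reading, since alteration is specified for MBL only.

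*No imbalance is shown.* This also stands. Shared entry criteria (age, need for maxillary implants, at least 6 months of edentulism, no untreated caries or periodontal disease) may limit it. A test at a pre-surgical visit, if there is one, would show a difference but would not correct later comparisons. By the figures above, it would detect a true difference of 0.2 to 0.5 SD only about 17% to 68% of the time.

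*The p-values carry no claim.* This stands and limits the consequence. A reader might take the rejection rates as an inflated false-positive rate for the trial, but the plan makes no decision on OHIP p-values. The bias in the group difference remains.

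*Adjustment changes the question.* Group is a pre-existing condition, and if low bone density affects oral status, starting OHIP may lie on the path to the outcome. Comparing OHIP after treatment is also a legitimate descriptive question, so it would go too far to say the secondary objective goes unanswered. However, the overall aim is to compare implant treatment between the groups, which favours accounting for the starting point. Keeping the raw comparison beside the adjusted one serves both questions.

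**Conclusion.** The point holds as a cheap improvement of low consequence. As written, the OHIP comparison has no protection against a starting difference between non-randomised groups. Under the assumed ranges the bias is 0.06 to 0.30 SD if the difference decays and 0.2 to 0.5 SD if it persists. Baseline adjustment brings this to 0 and 0.08 to 0.35 SD, so it reduces the bias without always removing it.

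The documents do not support saying that the groups differ, or that any difference is carried over in full. Nor is this an error in a confirmatory claim: OHIP is secondary and its p-values are not called significant. Other confounding would remain after adjustment. For example, the women know their diagnosis, and blinded assessment covers only the radiographic outcome.

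**What to change.** In Statistical methods and the visit descriptions:

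1. Name a pre-surgical OHIP (Visit 1 or 2) as the baseline. If it is not already collected, add the questionnaire at that existing visit.
2. Make the between-group OHIP comparison baseline-adjusted, by ANCOVA or rank ANCOVA, and report the adjusted difference with a 95% confidence interval.
3. Keep the unadjusted Wilcoxon test as a descriptive companion.

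The cost is a few sentences and at most one extra questionnaire. The downside is that the adjusted estimate depends on the model. If no pre-surgical OHIP can be obtained, the plan should say that the follow-up comparison cannot be corrected for starting differences.

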## Study timetable

Estimated date of first subject enrolled: November 2007  
 Estimated date of last subject completed: October 2016

